5.6 Data Analysis

5.6.1 Statistical Power for Primary Outcomes: We designed this pragmatic trial to achieve power of 0.9 for two primary outcomes at 12 months assuming 20% attrition. We target a two-sided type I alpha of 0.025 for each outcome to account for a Bonferroni correction. FOSQ: We plan to detect a meaningful and important difference for FOSQ between groups, 0.75 points,⁶⁵ and assume the known standard deviation for change in FOSQ of 2.5 points.^{65,79-82} We will retain power of 0.8, even with up to 39% attrition (Table 7). **Weight:** Participants in D-ELITE's self-directed arm lost 4.5 kg.⁴¹ Assuming weight loss in our comparator group is similar to average Veterans with OSA seeking weight loss, 1.2 kg,³³ we expect a 3.3 kg difference between groups.

This difference approximates a meaningful difference of 3% weight loss ([name] et al, JAMA, 2022, PMID: 36511927). Given known standard deviation in clinical weight change among Veterans' attempting weight loss of 6.9 kg/year,³³ we will have 0.99 power to detect this 3.3 kg difference in weight change with 20% attrition (Table 7). We will detect a 2.1 kg difference with power of 0.90. Similar to FOSQ, we retain power even with substantial attrition (Table 7).

Table 7. Power to detect differences in co-primary outcomes					
Change in Functional Outcomes of Sleep Questionnaire (FOSQ)					
Power	Alpha	SD (score)	Difference (score)	N	Attrition (%)
0.90	0.025	2.5	0.75	556	20
0.80	0.025	2.5	0.75	426	39
Change in Clinical Weight					
Power	Alpha	SD (kg)	Difference (kg)	N	Attrition (%)
0.99	0.025	6.9	3.3	556	20
0.90	0.025	6.9	3.3	220	68
0.80	0.025	6.9	3.3	170	76
0.90	0.025	6.9	2.1	556	20

5.6.2. Hypothesis Testing for Analyses of Trial Population: We will use intention to treat for analyses of primary and secondary outcomes of consented patients.

H1 (Primary Hypothesis): Lifestyle intervention will lead to greater weight loss and improvement in sleep-related quality of life at 12 months relative to usual care.

H2a (Secondary Hypothesis): Lifestyle intervention will lead to greater improvement in secondary outcomes measured at baseline and follow-up relative to usual care.

H2b (Secondary Hypothesis): Self-directed lifestyle intervention will lead to more favorable values for outcomes only collected at follow up (e.g., AHI, global ratings of change).

Using intention to treat, we will test primary (H1) hypothesis separately for each outcome (weight and FOSQ) using linear mixed effects model

$$Y_{ii} = \beta_0 + \beta_1 T_i + \beta_2 X_i T_i + \beta_3 Q_i + \beta_4 A_i + u_i + \epsilon_{ii}$$

which models for each patient i their measure for each outcome (FOSQ and weight separately), incorporating time of measurement T_j (0 or 12 months), treatment by time interaction $X_i T_j$, stratification variables Q_i , and adjustment variables A_i including age, gender, race, Charlson comorbidity index, and rurality. The model will include a random normal intercept u_i for each patient and a random normal error term ϵ_{ij} , all assumed independent. The variances of the ϵ_{ij} will be assumed different at baseline and 12 months. Here, β_0 is the average baseline FOSQ/weight among the control and treatment groups combined (assumed equal due to randomization), β_1 is the expected change in FOSQ/weight over time in the control group, and β_2 , the quantity of interest in hypothesis H1, is the expected difference in the change in FOSQ/weight over time between the treatment and control groups, or equivalently the expected difference between groups at 12 months. In secondary analyses, we will incorporate primary and secondary outcomes from each time point (baseline, 3, 12, and 21 months). We will use the same model to test secondary outcomes captured only at follow up, omitting baseline values.

Additional Analytic Subgroups:

- 1) Subgroups defined by each of the pre-specified strata.
- 2) Subgroups defined by gender.
- 3) Patients who are prescribed continuous positive airway pressure and use <4 hours per night in the 90 days before the outcome period
- 4) The subgroup of patients who are prescribed continuous positive airway pressure and use ≥4 hours per night in the 90 days before the outcome period.

5.6.3. Missing and Misclassified Data: Our pragmatic trial prioritizes outcome collection from EMR, including JLV and CAPRI, to reduce participant burden and enhance generalizability. While we attempt to minimize missingness and misclassification through efforts to optimize follow up survey completion and validated approaches to decrease measurement error,^{49,83} we anticipate missing data. We originally considered complete case analyses, but ultimately chose an approach based on linear mixed models and maximum likelihood that is valid under the missing at random assumption.⁸⁴ Linear mixed models impute missing outcome data implicitly within a hierarchical model, using individuals' baseline, adjustment, and stratification values. Missing values of covariates will be imputed using the chained equations approach (e.g. MICE),⁸⁵ using single imputation if missing rates are less than 5% and multiple imputation otherwise. We will carry out the recommended sensitivity analyses to the MAR assumption using methods based on pattern mixture models and imputation, by assuming a range of perturbations of imputed outcome values and assessing differences in model conclusions.^{85,86}

5.6.4. Analysis for Qualitative and Quantitative Evaluations of Implementation Process:

Reach, Effectiveness, and Maintenance: We will compare those with OSA who are invited to the trial and enroll vs. those who do not. We will assess effectiveness and maintenance of effectiveness at 12 and 24 months in the trial population (Section 5.6.1-5.6.2). We may also use VA administrative and PAP usage data from VA approved platforms (e.g., Somnoware) to assess predictors and consequences of receiving our intervention or other guideline-based therapies for OSA and obesity among Veterans nationwide who meet one or more inclusion criteria for the randomized trial.

Costs and Budget Impact Analysis: We will record intervention costs and conduct a budget impact analysis to establish a business case for future implementation, should the intervention be effective. We will compare mean cost differences between trial arms using linear models (Model 1) like our co-primary outcomes, ensuring model assumptions are met for cost data with appropriate transformations. Budget Impact Analysis: Should the intervention be effective, we will conduct a budget impact analysis to establish a business case for future implementation efforts. Analysts will apply the above estimates of higher or lower cost differences between the study arms to project costs for implementing the self-directed lifestyle program nationwide among all VA patients with obesity and OSA. Analysts will estimate the number of VA patients at each site with OSA and obesity who are likely to use our intervention if it were to be rolled out more broadly based on the trial's reach measures and facility-specific Veteran population projections from the VA Enrollee Health Care Projection Model (EHCPCM). Sensitivity analyses for subgroups or more targeted rollout strategies will potentially be developed based on discussion with VA operational partners.

Qualitative Data Analysis: We will analyze transcripts using simultaneous inductive and deductive content analysis.⁸⁷ Inductive content analysis consists of open (unstructured) coding,

allowing for the emergence of previously unidentified themes. In contrast, deductive content analysis is structured and consists of identifying themes that fit within *a priori* categories. *A priori* categories will be based on RE-AIM domains, and we will use quotes that do not accurately fit within existing *a priori* codes to iteratively develop novel codes. We may use ATLAS.ti analysis software for recording and managing codes. The project team will review the results of the analytic process to assess completeness.

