5.0 Study Procedures

5.1 Study Design

5.1.1. Proposed study design: POWER is a type 1 hybrid pragmatic RCT in which 696 Veterans with OSA and obesity will be randomized to usual care or usual care enhanced with the D-ELITE self-directed lifestyle intervention for 12 months. Our primary outcomes are change in sleep-related quality of life and weight at 12 months (Figure 4). We will assess secondary outcomes at 3, 12 and 21 months.

Figure 4.

We are also conducting an implementation process evaluation as described in 5.5.7.

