POWER staff will randomize each participant into the usual care or intervention group at a ratio of 1:1. Participants must have PCP clearance and completed baseline surveys before randomization can occur. Randomization should occur no more than sixteen weeks after the date of the index weight. After sixteen weeks we may ask the participant to return to the primary care clinic for a new index weight if still not randomized. We will notify participants of their randomization group via mail and/or email. The mailing will include a weight scale for all participants and the additional materials (DVDs and/or USB drives, instructional handouts, GLB curriculum, Calorie King Fat & Carbohydrate Counter, and paper tracking booklets) for intervention participants.

5.3.4 Stratification: Given three stratifying variables of BMI category (strata: 30-34.9 vs. 35-44.9 kg/m²), physiologic OSA severity (moderate to severe as defined by interpreting physician or apnea hypopnea index ≥ 15 events/hour vs. otherwise) and sleep related impairment (PROMIS Sleep Impairment T-score ≥ 60 vs. T-score < 60) there will be 8 strata. Stratification may help prevent covariate imbalance between groups.

5.3.5 Continuation of usual care: We will provide all control patients with the same weight scale as we provide to intervention patients. All participants will continue to receive standard care for OSA from their usual primary care and sleep providers. We chose usual care only for our control group because pragmatic RCTs are most useful in testing interventions in real-world settings and addressing the question “how does the intervention compare to what we are doing now?” We believe that including an alternate approach such as an attention control condition would undermine the purpose of this trial. Our study will not interfere with ongoing patient care, including referral to MOVE!, PAP prescriptions, or other sleep treatments. To protect external validity, no participant will be instructed not to seek weight loss or OSA treatment. We will include all participants in the intent to treat analysis. We will monitor electronic health record (EHR) data for participation in MOVE! and patient report for participation in non-VA weight loss programs. We will monitor PAP use through VA approved manufacturer-specific portals (Phillips Encore, ResMed AirView) as well as VA approved data management systems (e.g. Somnoware).⁵³

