5.4 Inclusion/Exclusion Criteria

Veteran Participant eligibility criteria: As we describe in more detail below, we will utilize the CDW to identify Veterans with recent sleep study and diagnosis of OSA with measured body mass index (BMI) between 30.0-44.9 kg/m² recorded in the past three months. Including patients with recent sleep study will increase likelihood of accurately identifying participants with OSA,⁶⁰ and will allow recruitment after initial diagnosis or reassessment when patients may be more amenable to behavior change interventions.⁶¹

To minimize spurious inclusion, we will ensure an additional BMI within the past 12 months of index weight that meets criteria set by a standard algorithm to remove implausible and erroneous BMI values.^{29,62,63} Specifically, we use the criteria used previously for the D-ELITE trial^{62,63} to exclude any index weight indicating excessive weight change prior to the index date: >40-pound change in any 30-day period in past year, or more than two pounds change per week over periods greater than 30 days. To exclude plausible but likely invalid index weights, we excluded weights if 1) the standard deviation of the difference between index and any past-year weight is greater than 5% of the average weight, 2) if the weight change is greater than ± 100 pounds in a year, or 3) if the BMI change is greater than ± 15 kg/m². We also exclude weights greater than 500 pounds or less than 90, height < 49 or > 84 in., and BMI greater than 65 or less than 15 kg/m² (calculated using the most recent height measurement between 49 and 84 in.). We apply the same algorithms for flagging potentially implausible and erroneous weights for outcome measurement (Section 5.5.2).

We will also confirm OSA by reviewing sleep studies, among those who have not opted out, prior to enrollment. We will calculate index and previous BMI using most recent height and weight. Exclusion criteria are chosen to ensure participant safety, while maximizing internal validity, and minimizing error caused by missing and misclassified data (Table 4).

Table 4: Inclusion and Exclusion Criteria

Inclusion

- Diagnosis of OSA on sleep study (sleep provider confirmed)
- Clinical BMI between ≥ 30 , $< 45 \text{ kg/m}^2$, and at least one additional plausible BMI in last 12 months
- Access to television and DVD player, computer with USB drive, or internet
- Able to participate fully in all study protocol/procedures including informed consent

Exclusion

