Methodology: We plan a hybrid type 1 pragmatic randomized controlled trial. We will proactively identify Veterans with OSA and obesity nationwide using data from the CDW (n=696), randomizing 1:1 to usual care plus the D-ELITE weight loss intervention or usual care alone. We will collect primary outcomes at 12-months, but we will also collect outcomes at 3- and 24-months to assess trends over time. For our implementation process evaluation, we will use quantitative and qualitative methods to assess barriers to implementation, including a comprehensive budget impact analysis.

2. Sample Size Rationale:

We designed this pragmatic trial to achieve power of 0.9 for two primary outcomes at 12 months assuming 20% attrition using a two-sample t-test of independent means (STATA version 16.1). We target a two-sided type I alpha of 0.025 for each outcome to account for a Bonferroni correction. FOSQ: We plan to detect an established meaningful and important difference for FOSQ between groups, 0.75 points, and assume the known standard deviation for change in FOSQ of 2.5 points. Weight: Participants in a prior version of the D-ELITE self-directed intervention lost 4.5 kg. Assuming weight loss in our comparator group is similar to average Veterans with OSA seeking weight loss, 1.2 kg, we expect a 3.3 kg difference between groups. This difference approximates a meaningful difference of 3% weight loss ([name] et. al., JAMA, 2022. PMID: 36511927). Given known standard deviation in clinical weight change among Veterans' attempting weight loss of 6.9 kg/year, we will have 0.99 power to detect this 3.3 kg

difference in weight change with 20% attrition (Table 1). We will detect a 2.1 kg difference with power of 0.90. Across both co-primary outcomes, we retain power of 0.8 even with 39% or more attrition (Table 1).

3. Description of how data will be collected:

We will enroll 696 Veterans nationwide. In CDW, we will identify Veterans with an eligible outpatient BMI and sleep study recorded in the past 6 months with associated diagnosis of OSA who are free from exclusionary conditions searchable in CDW.

- **Research invitation:** We will invite potentially eligible patients by mail and email, and will send an invitation letter, information statement, and an opt-in/out postcard and Qualtrics link.

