- **Telephone screen, consent, and baseline assessment:** Among those who do not opt-out, a research coordinator will review the patients' chart and will call to assess eligibility. Coordinators will describe the study in detail and obtain consent under a waiver of documentation of written informed consent. For those who consent, a research coordinator will administer baseline surveys over the telephone if possible.
- **Medical clearance:** After consent, but prior to randomization, we will send a secure email to each interested participant's primary care provider informing them of their patient's desire to participate. We will ask if their patient should not participate given the intervention content.

We will mail and email Veterans surveys at baseline and 3, 12, and 21-month follow-up. Research coordinators will administer surveys via telephone if they are not completed by mail or online through Qualtrics. We will assess baseline information using a health inventory checklist including socio-demographic characteristics, health behaviors, and non-VA weight loss programs. We will obtain additional information about comorbid conditions, medication use, healthcare utilization, and distance to clinics from the CDW.

Primary Outcomes: The co-primary endpoints for our pragmatic trial are changes in sleep-related quality of life and weight from baseline to 12 months. In secondary analyses, we will assess these outcomes at additional timepoints.

- **Sleep-Related Quality of Life:** FOSQ addresses domains that are important to patients: activity level, vigilance, intimacy/sexual relationships, productivity, and social outcome. FOSQ is sensitive to changes in OSA treatment and is widely used in trials of OSA management.
- **Weight Loss:** Consistent with the pragmatic nature of this trial, we will prioritize clinically measured weights using methods shown to be feasible and valid when compared to research weights. We will use participants' qualifying outpatient clinical weight prior to randomization as their baseline measure. To assess change, we will select the outpatient clinical weight that is closest to the 12-month post-randomization date within a 9–15-month post-randomization window, using a standard algorithm to remove implausible and erroneous values.

Contingency for weight:

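### The primary weight model could also use the earlier clinic weight that eligibility guarantees: a small, optional gain in precision, not an error

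*Protocol*

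**What the plan says.** **Model.** Protocol 5.6.2 and SAP 9 give one linear mixed model, fitted separately to weight and FOSQ at 0 and 12 months. It has a common baseline mean, a treatment-by-time term, a random intercept, and residual variances that differ between the two visits. Covariates are main effects: the stratification variables (BMI category, OSA severity, sleep-related impairment; SAP 7) and adjustment variables "including age, gender, race, Charlson comorbidity index, and rurality". No earlier weight is listed.

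**Baseline weight.** SAP 3 states: "We will use participants' qualifying outpatient clinical weight prior to randomization as their baseline measure". Protocol 5.5.2 places that reading within the four months before randomization.

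**Eligibility.** Protocol 5.4 states: "we will ensure an additional BMI within the past 12 months of index weight that meets criteria set by a standard algorithm". The inclusion table repeats the requirement. The same section excludes index weights that differ too much from past-year weights. Its rules include a cap at 5% of average weight on the standard deviation of the difference, and a cap of two pounds per week over periods longer than 30 days.

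**Power.** Protocol 5.6.1 states: "We designed this pragmatic trial to achieve power of 0.9 for two primary outcomes at 12 months assuming 20% attrition". On multiplicity it states: "We target a two-sided type I alpha of 0.025 for each outcome to account for a Bonferroni correction". SAP 2 says the power was found "using a two-sample t-test of independent means (STATA version 16.1"), so covariates earn no credit. For weight, with an SD of change of 6.9 kg, the stated power is 0.99 at 3.3 kg and 0.90 at 2.1 kg.

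**The concern.** The baseline for this co-primary outcome is one routine-care reading. Such a reading can catch a person at a temporary high or low, and the five adjustment variables say nothing about which. An earlier weight does. It precedes randomization, so assignment cannot affect it. It exists for every eligible participant, and the study has already extracted it to apply the screening rules.

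Adjusting for it would leave the treatment effect being estimated unchanged and could narrow its standard error. At stake is some precision on weight, which matters mainly if the true difference lies nearer 2.1 kg than 3.3 kg.

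**Working it through.** **1. Inputs from the documents.** The trial is one "in which 696 Veterans with OSA and obesity will be randomized", with assignment to the "usual care or intervention group at a ratio of 1:1". After 20% attrition, 696 × 0.8 = 556.8; the plan uses 556, or 278 per arm. SD of change is 6.9 kg and two-sided alpha is 0.025.

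**2. The plan's own power.** SE = 6.9 × √(2/278) = 0.585 kg. The critical value is 2.241.
- At 2.1 kg: 2.1/0.585 − 2.241 = 1.347, power 0.911 (noncentral t: 0.910; stated 0.90).
- At 3.3 kg: 3.3/0.585 − 2.241 = 3.397, power 0.9997 (stated 0.99).

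The stated figures reproduce.

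**3. What the model already uses.** With two visits, a random intercept and two residual variances supply three parameters for a covariance matrix with three distinct entries. With the common baseline mean, the 12-month comparison is in effect conditioned on the index weight. The right benchmark is therefore the variance of the 12-month weight given the index weight, not the raw variance.

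**4. Gain from averaging out reading error.** Let s be the SD of one clinic reading's error and d the SD of true drift between the two pre-randomization weights. Neither is in the documents, so both are assumed. When people differ in weight by much more than s, the index reading alone leaves error variance s². The best combination of both readings leaves s²(s² + d²)/(2s² + d²). The saving is s⁴/(2s² + d²), so

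cut in residual variance ≈ [s⁴/(2s² + d²)] / 6.9², where 6.9² = 47.61.

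| s (kg) | d = 0 | d = 2 kg | d = 4 kg |
|---|---|---|---|
| 1 | 1.1% | 0.4% | 0.1% |
| 2 | 4.2% | 2.8% | 1.4% |
| 3 | 9.5% | 7.7% | 5.0% |

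For example, s = 2 and d = 2 gives 16/(8 + 4) = 1.33, and 1.33/47.61 = 2.8%. Exact conditional variances with between-person SDs of 12 and 18 kg agree to within about one percentage point. With no reading error and a memoryless weight path the cut is zero.

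The extreme case treats all of the 6.9 kg as independent scatter: s = 6.9/√2 = 4.88 kg, with d = 0, so 11.9/47.61 = 25%.

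**5. Effect of the eligibility filter.** Read as a two-reading SD, the 5% rule caps the gap between the readings at 0.05 × 110 × √2 = 7.8 kg for a mean weight of 110 kg (assumed). Simulating that rule lowers the cut at s = 3 kg to 2.3–6.5%. It lowers the extreme case to 9.7% at d = 0, and to less with drift.

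**6. Other weight paths.** Further assumptions here are a between-person SD of 14 kg, reading error of 1.5–2.5 kg, and an earlier weight 3–9 months before the index weight. Simulation with both the 5% and the two-pounds-per-week rules gives a cut of about 0–3% if weight drifts as a random walk. If weight partly returns to a personal level (half-life 3–12 months), the cut is about 1–9%.

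**7. Consequence of a 0–10% cut at 278 per arm.**

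| Cut | SD (kg) | Power at 2.1 kg | Difference detectable at 0.90 power | Equivalent extra participants with data |
|---|---|---|---|---|
| 0% | 6.90 | 0.911 | 2.06 kg | 0 |
| 5% | 6.73 | 0.925 | 2.01 kg | 556/0.95 − 556 = 29 |
| 10% | 6.55 | 0.938 | 1.96 kg | 556/0.90 − 556 = 62 |

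Power at 3.3 kg stays above 0.999 throughout.

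**The case against.** The strongest reply is that nothing is wrong. The covariates are prespecified and defined, no passage contradicts another, and a plan need not use every prognostic variable. Most of the available precision is already taken through the index weight. At the expected 3.3 kg there is no power to recover, and the 2.1 kg row meets 0.90 without covariate credit. FOSQ drives the sample size, according to the SAP edit log for version 3.0, and gains nothing. That log also says the adjustment variables were published, so a change must be documented. All of this stands. It limits the point to an optional refinement but does not remove the small gain.

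A reader might infer three stronger things, which the documents do not support.
- **That the model ignores pre-randomization weight.** It does not: the index weight is the time-zero outcome and BMI category is a covariate.
- **That the gain could reach a fifth or a quarter of the variance.** That requires independent scatter of about 4.9 kg per reading, and the screening rules in Protocol 5.4 remove many people whose readings differ that much. With the filter the figure is 10% or less.
- **That a single baseline reading biases the comparison.** The reading is taken by the same rule in both arms before randomization, so its noise costs precision only.

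**Conclusion.** The omission is real and the planned analysis is sound. Adding the earlier weight would cut the residual variance of the weight comparison by roughly 0 to 10%, and the range includes almost nothing. Power at 2.1 kg would rise from 0.91 to at most 0.94, equivalent to no more than about 60 further participants with data. The expected 3.3 kg comparison and FOSQ would not change in any way that matters.

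The range rests on assumed values for reading error, drift, between-person spread, mean weight and lag, and on reading the 5% rule as a two-reading standard deviation. A reading as an absolute 5% difference would filter more strictly and shrink the gain further. The documents cannot narrow the range, but the trial's own pre-randomization weights could inform it without reference to treatment arm.

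**What to change.** In SAP 7 and 9 and Protocol 5.6.2, for the weight model only:
- Add the most recent plausible outpatient weight before the index weight, within 12 months of it.
- Give it a separate coefficient at each visit, because the other covariates enter as main effects and a single shared coefficient could miss a return towards a personal level.
- Include its lag to the index date.
- Make the change as a dated SAP edit before unblinding. The Protocol abstract says that analysis has not begun; if that point has since passed, keep the planned model as primary and report this one as a labelled sensitivity analysis.

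The earlier weight should not be entered as a third outcome row. Under the plan's random intercept, that row would assume the same covariance between visits whatever their spacing, and under random-walk drift it can slightly lose precision.

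The cost is a few extra parameters, a lag that varies between people, and a documented change to a published covariate list. No new data collection is needed.
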